Linear accelerator based CT imaging (CT on rails or cone beam CT) or re-CT-simulation will be performed after 45 Gy to assess for the need to re-plan secondary to response. Tumor size will be documented using recist criteria based on these images. Additional accelerator based CT imaging is acceptable as clinically indicated.

Definitive or palliative local therapy with surgery when indicated will be performed after completion of the combined regimens. If the patient is deemed operable the first follow-up visit will occur after surgery. If the patient is deemed inoperable the first follow-up visit will occur after concurrent Capecitabine and radiation therapy. Subjects will be followed every 3 months (+/- 1 month) post treatment times 1, then every 6 months (+/- 1 months) times 1, then every 12 months (+/- 2 month) times 2. PET/CT scan or ultrasound will be performed in conjunction with the first follow up visit. For patients treated to definitive dose for gross unresected disease (any treatment field receiving a total of > 60 Gy in the mosaic prescription), all sites receiving > 60 Gy will be scored as complete response, partial response, noresponse/progressive disease based on imaging and exam after this visit and when evaluable and all subsequent visits. Subsequent radiologic studies will be at the discretion of the treating oncologist as dictated by standard of care. Toxicity will be recorded at each visit using the RTOG criteria.

Capecitabine dose reduction criteria are as follows:

Capecitabine will be held for patients experiencing grade 3-4 Capecitabine related

toxicities until symptomatic improvement (Grade 1). Radiation therapy will not be held for Capecitabine related toxicities. Patients will then be restarted with reduced dose of Capecitabine (level-1). Level -1 (25% dose reduction) = 600 mg/m^2 BID. If patients develop additional grade 3-4 toxicity in spite of dose reduction, the chemotherapy will be permanently discontinued.

Correlation will be made between Change in CTC level and change in percent of CD44+CD24lo or ALDH1+ cells in the tumor biopsy. Change will be correlated with clinical and pathologic response (in patients who undergo surgery)

Approximately 60 subjects will be enrolled. Assuming an average accrual rate of 3-4 subjects per month, the duration of accrual will be approximately 20 to 26 months.

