### **11.3 Sample Size Considerations and Interim Analyses**

The primary objective of this study is to determine the efficacy of pre-operative radiation with concurrent capecitabine in patients who have experienced a minimal response or progression after standard neoadjuvant chemotherapy. Efficacy will be determined by tumour response (complete response + partial response) as measured by RECIST criteria. Tumour response will be assessed after 45 Gy. Those who do not finish will be considered non-responders. Toxicity will be assessed at the same time. Surgical complications will be assessed independently within 6 weeks of surgery. Only grade three toxicity will be considered in the stopping rules. This study will be monitored for both efficacy and safety. Safety will be determined by the rate of grade 3 or higher toxicities, excluding acute skin toxicity. This regimen will not be considered of interest for further study if there is a high probability that the response rate is less than 80% or the severe toxicity rate is greater than 20%. Priors regarding response are based on combined retrospective data from three studies of 135 total patients treated for gross disease in the breast at our institution and detailed in the background (sections 3.2 and 3.5). Local control (a surrogate for response) at 5-years in patients treated for gross IBC disease in the breast with radiation alone was 75% (N = 42, unpublished). In 38 similar patients with non-inflammatory breast cancer local control was 70% at 5 years. In an unpublished retrospective analysis of 55 patients treated with the regimen proposed herein, 5-year local control was 85% (Perkins, SABCS abstract, 2007). There are limited and poor data regarding radiation alone toxicity in this exact cohort. The priors for toxicity were based on aggressive xrt in post-mastectomy patients (N = 192). In these patients, we expect a 15% rate of Grade 3 toxicities in patients receiving 60Gy and a 29% rate of Grade 3 toxicities in patients receiving 66Gy, and unpublished data. Clinically we are currently limiting the use of the latter regimen based on the impression that this is unacceptably high toxicity, so we are targeting a Grade 3 toxicity rate of no more than 20%. All patients who receive any treatment will be included in the analyses of both efficacy and safety. Patients who are not evaluable for response will be considered non-responders. The final analysis will be an Intent to Treat analysis. A total of 60 patients will be enrolled at the rate of 3-4 patients per month. Stopping boundaries will be assessed in cohorts of 5 patients after a minimum of 10 patients have been enrolled. Response and toxicity will be monitored independently. The method of Thall and Simon will be employed to perform interim monitoring.

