##### **11.6.1 Primary Analysis**

The primary endpoint in this study is response defined as the percentage of subjects achieving a complete or partial tumor response using RECIST criteria. The response rate will be calculated from the view of best response that records confirmed cases of CR or PR. Subjects with unknown or missing response will be treated as non-responders; i.e., they will be included in the denominator when calculating the percentage. Response will be evaluated by the recist criteria 4 weeks (+/- 4 days) after completion of radiation therapy.

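### Sections 6.0, 11.3 and 11.6.1 disagree on when the primary response is read: section 6.0 schedules no scan for the 4-week RECIST evaluation and, in operable patients, no second scan before surgery to confirm a response

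*Combined protocol and SAP*

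**What the plan says.** Three sections bear on when response is read.

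- **11.6.1 Primary Analysis** gives the time: "Response will be evaluated by the recist criteria 4 weeks (+/- 4 days) after completion of radiation therapy". It also restricts what counts: "The response rate will be calculated from the view of best response that records confirmed cases of CR or PR". Unknown or missing responses stay in the denominator as non-responders.
- **11.3 Sample Size Considerations and Interim Analyses** gives a different time: "Tumour response will be assessed after 45 Gy". Toxicity is assessed at that same point, and patients not evaluable for response count as non-responders.
- **6.0 Study Design** schedules the imaging. During treatment, "Linear accelerator based CT imaging (CT on rails or cone beam CT) or re-CT-simulation will be performed after 45 Gy", and "Tumor size will be documented using recist criteria based on these images". After treatment, "PET/CT scan or ultrasound will be performed in conjunction with the first follow up visit". On when that visit falls: "If the patient is deemed operable the first follow-up visit will occur after surgery"; for inoperable patients it comes after chemoradiation, with no week given. The only numbered interval is: "Subjects will be followed every 3 months (+/- 1 month) post treatment times 1".

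The baseline RECIST measurement is made on the planning CT (sections 4.2 and 6.0). The Time and Events Table (Appendix E) and the RECIST rules (Appendix F) are cited but are not in the supplied text.

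**The concern.** The time at which 11.6.1 reads the primary endpoint has no matching scan in section 6.0. The one scheduled reading that certainly precedes surgery, the CT after 45 Gy, is taken during treatment and so cannot also be the 4-week reading. For a patient who goes to surgery, the next scheduled imaging comes after the operation. By then a resected target lesion can no longer be measured. That imaging is also PET/CT or ultrasound, whereas the baseline is a planning CT.

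Confirmation has the same gap. A single reading cannot normally confirm itself, and section 6.0 schedules no second one before surgery. Choosing 45 Gy as the governing time would settle the timing but not this.

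The loss may be related to the outcome. One of the two routes to conversion in section 11.6.2 requires objective clinical response together with mastectomy performed or offered. Where patients reach surgery by that route, those without a 4-week reading would tend to be responders, and the missing-as-non-responder rule would score them against the regimen.

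**Working it through.** **1. Do the two windows overlap?**
- 11.6.1: 28 - 4 = day 24 to 28 + 4 = day 32 after radiation.
- 6.0: 3 months +/- 1 month is 2 to 4 months. At 30.44 days per month, that is about day 61 to day 122.
- The windows do not overlap; the gap is about 61 - 32 = 29 days. Section 6.0 gives no week for the first follow-up visit other than this interval, and the documents state no interval from radiation to surgery.

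**2. Scheduled readings before surgery in an operable patient (body text only)**

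| Reading | Before surgery? | Meets the 11.3 time? | Meets the 11.6.1 time? |
|---|---|---|---|
| CT after 45 Gy | Yes | Yes | No, on treatment |
| 4 weeks after radiation | Not scheduled in 6.0 | No | Yes, if done |
| First follow-up PET/CT or ultrasound | No | No | Only if the visit falls on days 24-32; the target lesion may be resected |

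This leaves one scheduled pre-surgical reading, none at the 11.6.1 time, and no scheduled pair for confirmation.

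**3. Reproduce the plan's own interval**
The prior for response is beta(1.6, 0.4) (section 11.3.1). With x responses in 60, the posterior is beta(1.6 + x, 0.4 + 60 - x). For x = 54 this is beta(55.6, 6.4), with 2.5% and 97.5% points of 81.06% and 95.89%. The plan prints 81.1% and 95.9% (section 11.3.3), so it is reproduced. The printed response and toxicity boundaries were also recovered at all 11 looks.

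**4. Effect of lost readings on the final estimate**
The documents do not say how many patients would lack a qualifying reading, so the losses below are assumptions. Suppose 54 of 60 truly respond and L of those responders are scored as missing:

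| L (assumed) | Scored responders | Observed rate | Posterior | 95% interval |
|---|---|---|---|---|
| 0 | 54 | 54/60 = 90% | beta(55.6, 6.4) | 81.1-95.9% |
| 6 | 54 - 6 = 48 | 48/60 = 80% | beta(49.6, 12.4) | 69.3-88.9% |
| 15 | 54 - 15 = 39 | 39/60 = 65% | beta(40.6, 21.4) | 53.3-76.7% |

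Section 11.1 calls the regimen of interest if the response rate is at least 80%. Six lost responders bring a 90% rate down to that threshold, and fifteen take it well below.

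**5. How many patients could be exposed?**
Section 3.5 reports conversion to operable in 91% of an institutional series of 55 and in 23/28 = 82% of a published phase II study. These figures suggest that surgery may be common. They are not the share who would be operated on without a 4-week reading.

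**The case against.** The strongest reply is that a pre-surgical reading does exist. Section 6.0 requires a CT after 45 Gy with RECIST size recorded, without limiting it to a subgroup, and 11.3 names that point as the response assessment. This stands. A reader might infer that operable patients have no valid primary-endpoint reading at all; that is true only under the timing in 11.6.1. The conflict between 11.3 and 11.6.1 is the root of the problem.

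A reader might also infer that the stopping rule would fail. On the printed response boundary alone, with a true rate of 80%, the chance of stopping before 60 patients is 8%. It would become 41%, 82% or 93% if 10%, 20% or 25% of responders went unread (observed rates 0.80 x 0.90 = 72%, 0.80 x 0.80 = 64%, 0.80 x 0.75 = 60%). Those loss fractions are assumed, and the boundary belongs to 11.3, where response is read after 45 Gy. On that text surgery removes no interim reading. The figures apply only if monitoring in fact uses the 4-week reading.

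Three further inferences are not supported:

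- **That the lost patients are the best responders.** The second conversion route in 11.6.2 does not state a need for objective response, and the trial also enrols palliative, oligometastatic and recurrent disease.
- **That post-surgical imaging would be scored as a complete response.** Nothing assigns that imaging to the primary endpoint. Its stated uses are the 3-month PET criterion for conversion and the scoring of unresected sites above 60 Gy. RECIST measurements are made by a single physician, so variation between readers is not the issue either. What remains is that the plan has no rule excluding such imaging.
- **That the visit schedule as a whole lacks a 4-week visit.** Appendix E might contain one, and Appendix F might define confirmation. A 4-week scan before surgery is unscheduled in section 6.0, not excluded.

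The mismatch in the body text survives all of this.

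**Conclusion.** The concern holds for the final response estimate, conditionally. As supplied, sections 6.0, 11.3 and 11.6.1 cannot all be followed: they give two response times, and only the 45 Gy time has a scheduled scan. They also impose a confirmation requirement with no second scheduled pre-surgical reading in operable patients.

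The bias is downward if patients without a qualifying reading are scored as missing. Its size cannot be fixed from the documents. The illustration runs from no loss (90%) to 80% with six lost responders and 65% with fifteen. It rests on three assumptions: 11.6.1 governs the final analysis, the missing rule is applied as written, and the lost patients are responders. If every patient is read before resection, at the stated time and with confirmation defined, the plan's 81.1-95.9% example stands unchanged. The interim rule is not shown to be affected while monitoring uses the 45 Gy reading.

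**What to change.** Reconcile sections 6.0, 11.3, 11.6.1 and Appendix E:

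1. State which reading is the primary response, and which reading feeds interim monitoring if the two differ.
2. Put the 4-week (+/- 4 days) RECIST evaluation that 11.6.1 already requires into the schedule, using imaging comparable to the baseline planning CT and read before resection where surgery has not yet taken place. Surgical timing should not be altered for it.
3. State that imaging after resection of a target lesion is not used for RECIST response, and that the last pre-surgical CT is used if surgery comes first.
4. State which pre-surgical readings satisfy the confirmation requirement (for example, after 45 Gy and at 4 weeks), or drop the requirement, and align this with Appendix F.
5. Keep the first follow-up PET/CT or ultrasound for its existing follow-up purposes.

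The cost is protocol wording and, if Appendix E does not already have it, one line in the Time and Events Table. No evaluation is added beyond what 11.6.1 requires; the small downside is having to book that scan before surgery. A reading missed before resection cannot be recovered afterwards.

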#### i. Efficacy

The secondary efficacy objectives of the study are:

- To determine the rate of conversion to operable, cCR, and pCR after completion of all protocol specified therapy. This includes the following:
  - Pre-operative concurrent radiation with capecitabine to the breast and at risk or involved regional lymph node basins
- To determine locoregional control of unresected nodal disease treated to definitive radiation dose ( $\geq 60\text{Gy}$ )

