### **3.2 Pre-operative breast radiation alone**

Treatment of non-metastatic/oligometastatic IBC and locally advanced non-IBC consists of neoadjuvant chemotherapy, mastectomy and axillary lymph node dissection, followed by adjuvant radiation. In patients with progressive disease during neoadjuvant chemotherapy, widespread metastatic disease at presentation, and inoperable disease either at presentation or after neoadjuvant chemotherapy, or gross in breast/chest wall recurrence, pre-operative radiation is a component of appropriate standard of care to achieve tumor and symptom control and potentially render patients operable. Local control in 42 IBC patients treated at MDACC with pre-operative or definitive radiation for gross disease (40/42 without concurrent chemotherapy) was 75% at 5 years. Distant metastasis free survival was 20% with 8 patients alive without evidence of distant metastasis at  $\geq 40$  months of follow up (range among women alive without evidence of disease 40 – 240 months, unpublished data).

Among 38 non-IBC patients treated with radiation for inoperable breast cancer resistant to anthracycline-containing primary chemotherapy on five consecutive MDACC institutional trials without evidence of distant metastases at diagnosis revealed thirty-two (84%) of the 38 patients were able to undergo mastectomy after radiotherapy. For the whole group, the overall survival rate at 5 years was 46%, with a distant disease-free survival rate of 32%. The 5-year survival rate for patients who were inoperable because of primary disease extent was 64% compared with 30% for those who were inoperable because of nodal disease extent ( $p = 0.0266$ ). The 5-year rate of locoregional control was 73% for the surgically treated patients and 64% for the overall group. Of the 32 who underwent mastectomy, the 5-year rate of significant postoperative complications was 53%, with 4 (13%) requiring subsequent hospitalization and additional surgical revision. Preoperative radiation doses of  $\geq 54$  Gy were significantly associated with the development of complications requiring surgical treatment (70% vs. 9% for doses  $< 54$  Gy,  $p = 0.0257$ ).

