2. 57 Gy at 1.8 Gy per fraction (IMRT) with optional nested GTV dose to total not to exceed 72 Gy at 2.2 Gy per fraction (Example Figure 1), or
3. 51 Gy at 1.5 Gy per fraction twice daily (bid) to the CTV followed by optional GTV boost at 1.5 Gy bid to total dose.

Dose escalation  $\geq 60$  Gy to achieve local control of gross disease that will not be resected (patient remains inoperable in surgical consultation prior to completing radiation treatment. patient has gross disease in sites not resected in standard surgery such as IMC nodes and supraclavicular nodes) will be at the discretion of the treating physician (See example, Figure 1)

*Guidelines for GTV dose escalation:*

- 60-66Gy to gross disease  $<1$  cm, up to 72 Gy to gross disease  $\geq 1$  cm when standard normal tissue constraints can be met) can be delivered to regional lymph nodes that will not be resected at the time of surgery.
- Based on the data by Huang et al 3, dose to potentially resectable disease (that routinely removed in a modified radical mastectomy: breast and level I/II lymph nodes) will be limited to 54 Gy at 2 Gy/fraction or 57 Gy at 1.8/fraction to limit surgical complications in operable patients.

Dose regimen (of the three listed options above) will be at the discretion of the treating oncologist. Nearing the conclusion of 50-54/57/51 Gy patients will be reassessed for operability by the attending physicians and/or the surgeon.

Protocol based radiation dose to the CTV incorporates regimens in current practice. While an argument for a palliative dose strategy such as 30 Gy in 10 fractions of 3 Gy per fraction could be made for this population, there is little to no data using Capecitabine with fraction sizes larger than 2.0 Gy per fraction, and it has been suggested by the gastro-intestinal radiation service at MDACC 13 that higher dose is needed to effectively test a radiosensitizer. .

Treatment will be continued on the basis of tumor reassessment and/ or disease status

performed at 1 week intervals. All radiation planning will be peer-reviewed in a weekly breast radiation planning QA conference. Radiation to a second site (metastatic disease excluding whole brain) during or overlapping with protocol specified therapy is permitted.

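### Locoregional control of unresected nodes is never defined, and its only scoring scale merges non-response with progression and omits nodes given exactly 60 Gy

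*Combined protocol and SAP*

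**What the plan says.** Section 1.0 (i. Efficacy) lists as a secondary aim "To determine locoregional control of unresected nodal disease treated to definitive radiation dose", with the dose given as 60 Gy or more. Section 10.0 repeats it among the secondary endpoints. Neither place gives a failure event, a time point or an estimator.

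The only assessment described is in section 6.0. It applies to "any treatment field receiving a total of > 60 Gy in the mosaic prescription" and states that all such sites "will be scored as complete response, partial response, noresponse/progressive disease based on imaging and exam after this visit". Scoring starts after the first follow-up visit and is repeated at later visits when the site is evaluable. PET/CT or ultrasound accompanies the first follow-up visit. After that, "Subsequent radiologic studies will be at the discretion of the treating oncologist as dictated by standard of care".

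Sections 11.5 to 11.7 contain no analysis of this endpoint. Section 11.6.2 covers conversion to operable, pCR and the response rate in evaluable patients. There, stable and progressive disease are separate categories.

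**The concern.** Control of irradiated disease ordinarily means that it has not progressed. On that meaning a stable node is a success and a growing node is a failure, yet the scale gives both one label. The plan depends on this scale because it offers no other definition or analysis. What is at stake is whether a stated secondary objective can be answered for the nodes where the answer is least obvious, namely those that never shrink enough to be called a response. Such nodes are plausible here, since section 6.0 enrols disease that has progressed, persisted or responded little to chemotherapy.

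The set of sites scored also differs from the set the objective names. The objective is about nodes at 60 Gy or more. The scoring is about any unresected site above 60 Gy.

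**Working it through.** The plan states no target rate, sample size or precision for this endpoint, so there is no figure to reproduce. The check is a comparison of the text plus a bound.

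**1. What the plan means by control.** Section 3.2 reports it as a rate over time: "The 5-year rate of locoregional control was 73% for the surgically treated patients and 64% for the overall group". Section 3.5 gives, for the 55 patients treated with capecitabine and radiation, a clinical complete response rate of 33%, one patient with progressive disease, and 5-year LRFFS of 85%. Section 11.3 cites 85% as 5-year local control for a 55-patient series on the same regimen. The plan's own usage therefore keeps control apart from response and closer to freedom from failure.

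**2. Bound from the joint category.** At one visit, let the shares of scored nodal sites be CR, PR and q (the joint category), with CR + PR + q = 1. Write q = s + f, where s is stable and f is progressive.

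- Control as no progression: C = 1 − f = CR + PR + s.
- Only q is recorded, so f can be anything from 0 to q, and 1 − q ≤ C ≤ 1.

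The documents give no value for q, so it is an assumption:

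| q | Control at that visit |
|---|---|
| 10% | 90% to 100% |
| 20% | 80% to 100% |
| 30% | 70% to 100% |

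The width of the interval equals q.

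**3. What repeat scoring recovers.** A site that moves from CR or PR into the joint category has visibly worsened. If a share r of all sites has done so and is counted as failed, then r ≤ f ≤ q and 1 − q ≤ C ≤ 1 − r. For example, with q = 30% and r = 10% (both assumed), control lies between 70% and 90%. At the first scoring there is no earlier score on this scale, so r = 0 and the full width remains. A site that is stable at first and grows later never changes label, so the time of its failure is lost too.

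**4. Which sites are scored.**

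- Dose: the objective includes 60 Gy, while section 6.0 requires more than 60 Gy. The section 4.1 guideline for unresected regional nodes begins at "60-66Gy to gross disease" under 1 cm, so exactly 60 Gy is an allowed dose. Such a node is in the objective and outside the scoring.
- Location: section 4.1 also allows escalation when the "patient remains inoperable in surgical consultation prior to completing radiation treatment", so breast or chest-wall sites can be scored as well as nodes.

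**5. Length of observation.** Nominal follow-up is 3 + 6 + 12 + 12 = 33 months. Suppose survival is exponential and resembles the background series (46% at 5 years in section 3.2, 48% in section 3.5). Then survival to 33 months is 0.46^(33/60) = 0.65 to 0.48^(33/60) = 0.67, so about a third would die first. Those are whole-cohort retrospective figures, not figures for the definitive-dose subset. They show only that death before nodal failure is common enough to need a stated rule.

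**The case against.** The strongest reply is that control might simply mean CR or PR. Section 11.3 calls local control a surrogate for response, and on that definition the rate is exactly 1 − q and can be read from the scale. This stands as a possibility, so the root gap is the missing definition. It does not remove the point, because the plan nowhere adopts that definition and its background sections use control differently.

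The slash could also be read as separating two labels. Appendices E, F and G were not in the text available to me, and a form there might record stable and progressive disease separately. If so, section 6.0 should say so. The point concerns the scale as section 6.0 words it.

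Finally, this is an unpowered, descriptive endpoint in a subset defined by an optional boost. It touches neither the primary endpoint nor the stopping rules. That is correct and limits the weight of the point.

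A reader might also infer three stronger things that the documents do not support:

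- That control cannot be derived at all. It can under a CR + PR definition, and worsening after CR or PR is visible.
- That non-nodal sites contaminate the result. Scoring is by site and nothing says the scores are pooled. Nodal sites can be selected if the site type is recorded, which the text does not state either way.
- That the result will wrongly be set against the 5-year control rates. Section 11.3 uses those rates as the basis for the priors on response, and no such comparison is planned for this endpoint.

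**Conclusion.** The concern holds in a limited form. Locoregional control of unresected nodes is undefined. Under the usual meaning of no progression, the section 6.0 scale as written cannot separate controlled from failed nodes among those never scored CR or PR. The resulting uncertainty at a visit equals the share of sites in the joint category, less any share already seen to worsen after CR or PR. At first scoring it is 10 percentage points if q = 10% and 30 if q = 30%. These values of q are assumptions, and the conclusion depends on reading the slash as one category and control as absence of progression.

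Separately, the two dose thresholds disagree at exactly 60 Gy and must be reconciled. The point deserves correction because the change is small and serves a stated objective. It does not threaten the trial's main conclusions.

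**What to change.** - In section 6.0, replace the joint category with two: stable and progressive.
- Record each scored site as nodal or non-nodal, and use only unresected nodal sites for this objective.
- In sections 10.0 and 11.6.2, define control as no progression in the irradiated node.
- Reconcile the dose threshold that selects sites for scoring in section 6.0 with the one in the objective, so that both describe the same nodes.
- Report nodal failure descriptively over the nominal 33 months, with death before failure counted as a competing event.
- Report each later score with its assessment method (imaging or examination alone).

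The cost is one category, one site field, a note of the assessment method and a short analysis paragraph. No extra visits or scans are required. The downside is that there will be few sites and wide limits. Because imaging after the first follow-up visit is discretionary, separating stable from progressive disease at later visits may rest on examination alone, and the report should say so.
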